11.2.1. Missing data

Missing dates and times in the AE data will be handled as described in Section 11.10.1. Concentrations that are below limit of quantification (BLQ) in the PK data will be handled as described in Section 11.9.2.

There will be no imputations of other missing data. All subjects will be included into the safety analyses as far as the data permit.

11.3. Study populations

11.3.1. Safety analysis set

The safety analysis set will include all subjects who received at least one dose of ticagrelor and for whom any safety post-dose data are available.

Unless otherwise stated the safety analysis set will be used for the presentation of all demographic and disposition data, as well as all safety analyses. Exposure to IMP will also be presented using the safety analysis set.

11.3.2. Pharmacokinetic analysis set

The PK analysis set will consist of all subjects in the safety analysis set for whom at least one of the primary PK parameters, for a given analyte, can be calculated for at least two treatment periods (where one of the treatment periods needs to be the period in which the subject received the Reference product [Treatment C]), and who have no major protocol deviations thought to impact on the analysis of the PK data.

Subjects may be excluded from the PK analysis set as a result of the following:

- Data from subjects who experienced vomiting during the course of the study may be deleted from statistical analysis if vomiting occurred at or before median t_{max}
 - Clinical PK of ticagrelor are described in Section 5.2.
- Data from subjects for whom the pre-dose concentration is > 5% of C_{max} for ticagrelor in a specific treatment period

A subject may be excluded from the analysis only for the specific treatment period in which the AE occurred.

The exclusion of any subjects or time-points from the calculation of the PK parameters will be documented by the PK Scientist including the reason(s) for exclusion.

The available concentration data and PK parameter data for any subjects excluded from the PK analysis set will be listed only. Concentration data for subjects excluded from the PK analysis set will be presented in the individual figures of concentration versus time plots.

11.4. Determination of sample size

Based on the estimated within-subject coefficient of variation (CV) for C_{max} and $AUC_{(0-t)}$ of ticagrelor and AR-C124910XX of less than or equal to 24%, 30 evaluable subjects are needed to achieve a power of 90% that a two-sided 90% confidence interval (CI) for the ratio of C_{max} between two different ticagrelor treatments will totally be contained within the 0.8-1.25 limit.

Forty-two subjects will be randomized to a 6 sequence Williams square design for 3 periods and 3 treatments: ABC, BCA, CAB, ACB, BAC and CBA, in order to ensure at least 30 evaluable subjects at the end of the last treatment period.

11.5. Protocol Deviations

Protocol deviations are considered any deviation from the clinical study protocol relating to a subject, and include the following:

- Inclusion/exclusion criteria deviations
- Dosing deviations (e.g., incorrect treatment received, subject was not fasted as per the protocol requirements prior to and after dosing)
- Time window deviations for safety and/or PK assessments
- Subjects receiving prohibited concomitant medications
- Other procedural and study conduct deviations recorded by the clinical unit on a protocol deviation log

The criteria for the assessment and reporting of protocol deviations will be stipulated in a separate study-specific protocol deviation specification (PDS) document. This will include a Windows Allowance Document (WAD) which stipulates tolerance windows for safety and PK assessments. Measurements performed within these tolerance windows will not be considered as protocol deviations and will not be reported.

All protocol deviations will be discussed at the data review meeting prior to database hard lock in order to define the analysis sets for the study.

Important protocol deviations will be listed by subject.

Protocol deviations will be handled in accordance with PAREXEL SOPs.

For handling of protocol amendments, see Section 3.6.

11.6. Subject disposition

Subjects and/or data excluded from the PK analysis set will be listed including the reason for exclusion. Subject disposition will be summarized and will include the following information: number of subjects randomized and dosed, number and percentage of subjects completing the study and the number and percentage of subjects who were withdrawn (including reasons for withdrawal). Disposition data will be presented based on all subjects randomized.

Subject discontinuations will be listed including the date of study exit, duration of treatment and reason for discontinuation. A listing of informed consent response will also be presented.

11.7. Demographic and baseline data

Demographic variables (age, gender, race, ethnicity, height, weight and BMI) will be listed by subject. Demographic characteristics (age, gender, race and ethnicity) and subject characteristics (height, weight and BMI) will be summarized separately by treatment sequence and for all subjects in the safety analysis set. The denominator for percentages will be the number of subjects in the safety analysis set for each treatment sequence or for all subjects as applicable.

Medical history data will be listed by subject including visit, description of the disease/procedure, Medical Dictionary for Regulatory Activities (MedDRA) System Organ Class (SOC), MedDRA preferred term (PT), start date, and stop date (or ongoing if applicable).

A summary of the number and percentage of subjects who had relevant medical histories will be presented by treatment sequence and for all subjects for the medical history PT.

11.8. Prior and concomitant medication and drug administration

11.8.1. Prior and concomitant medication

Prior medications are those that started and stopped prior to the first dose of IMP; all medications taken after first dosing are considered as concomitant (including medications that started prior to dosing and continued after).

Prior and concomitant medication will be listed by subject and will include the following information: reported name, PT, the route of administration, dose, frequency, start date/time, duration and indication. Prior and concomitant medication will be coded according to the sponsor's drug dictionary.

11.8.2. Drug administration

Drug administration dates and times will be listed for each subject and treatment period.

11.9. Pharmacokinetic analysis

11.9.1. Pharmacokinetic parameters

Where possible, the PK parameters will be assessed for ticagrelor (parent) and its active metabolite AR-C124910XX on plasma concentrations.

Primary PK parameters

C_{max} Maximum observed plasma concentration

AUC_(0-t) Area under the plasma concentration-time curve from time zero to time

of last quantifiable analyte concentration

AUC Area under plasma concentration-time curve from zero to infinity

Secondary PK parameters

t_{max} Time to reach maximum observed concentration

 $t_{1/2}\lambda_z$ Half-life associated with terminal slope (λ_z) of a semi-logarithmic

concentration-time curve

kel Elimination rate constant
MRT Mean residence time

 MRC_{max} Ratio of metabolite C_{max} to parent C_{max} ,

adjusted for differences in molecular weights

MRAUC_(0-t) Ratio of metabolite AUC_(0-t) to parent AUC_(0-t).

adjusted for differences in molecular weights

MRAUC Ratio of metabolite AUC to parent AUC, adjusted for differences in molecular weights

The following diagnostic parameters will be listed, but not summarized:

 λ_z upper and The time interval (h) of the log-linear regression to determine $t_{1/2}$

lower

 λ_z , N Number of data points included in the log-linear regression analysis Rsq adj Regression coefficient adjusted for λ_z , N, Goodness of fit statistic for

calculation of λ_z

%AUC_{extrap} Percentage of AUC obtained by extrapolation, calculated as

 $[(C_{last}/\lambda_z)/AUC*100]$ where λ_z refers to the terminal elimination rate constant and C_{last} to the drug concentration at last observed time-point

Additional PK parameters may be determined where appropriate.

11.9.2. Derivation of pharmacokinetic parameters

The PK analyses of the plasma concentration data for ticagrelor and its active metabolite, AR-C124910XX, will be performed by Covance, on behalf of Clinical Pharmacokinetic Alliance, AstraZeneca Research and Development.

PK parameters will be derived using non-compartmental methods with Phoenix[®] WinNonlin[®] Version 6.3, or higher and/or SAS[®] Version 9.2, or higher. All descriptive and inferential statistical computations will be performed using SAS[®] Version 9.2, or higher.

PK analysis will, where possible, be carried out using actual times recorded in the raw data. If actual times are missing, nominal times may be used.

Plasma concentrations BLQ from the time of pre-dose sampling (t=0) up to the time of the first quantifiable concentration will be set to a value of zero. After this time-point, BLQ plasma concentrations will be set to missing for all concentration profiles. Where two or more consecutive concentrations are BLQ at the end of a profile, the profile will be deemed to have terminated and therefore any further quantifiable concentrations will be set to missing for the calculation of the PK parameters unless it is considered to be a true characteristic of the profile of the drug.

If an entire concentration-time profile is BLQ, the profile will be excluded from the PK analysis.

Terminal elimination half-life, estimated as $(ln2)/\lambda_z$, where λ_z refers to the terminal elimination rate constant, estimated by log-linear least squares regression of the terminal part of the concentration-time curve. For the determination of λ_z , the start of the terminal elimination phase for each subject will be defined by visual inspection and will be the first point at which there is no systematic deviation from the log linear decline in plasma concentrations. A minimum of 3 data points will be used in calculating λ_z , and the duration of time over which λ_z is estimated will be at least twice the subsequently estimated terminal half-life. Where an elimination half-life is estimated over less than two half-lives, it will be flagged, commented upon in the study report and interpreted with caution. AUC is estimated by $AUC_{(0-t)} + C_{last}/\lambda_z$ where C_{last} is the drug concentration at last observed time-point.

AUC values where the percentage extrapolation is less than 20% will be reported. The AUC values where the percentage extrapolation is greater than 20% will be flagged in the data listings.

AUCs will be calculated using the linear trapezoidal method when concentrations are increasing and the logarithmic trapezoidal method when concentrations are decreasing.

The minimum requirement for the calculation of AUC will be the inclusion of at least three consecutive plasma concentrations above the lower limit of quantification (LLOQ), with at least one of these concentrations following C_{max} .

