6.1. Primary objective

• To evaluate bioequivalence of ticagrelor OD tablets when administered with water and without water, compared to ticagrelor IR tablets

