11.9.4. Statistical analysis

The statistical analysis will be conducted separately for the following:

- Treatment A versus Treatment C
- Treatment B versus Treatment C

Only the data for the comparison under investigation will be included in the statistical analysis i.e., when comparing Treatment A and Treatment C, the data for Treatment B will be removed from the dataset.

Subjects must have the primary PK parameter (C_{max} , $AUC_{(0-t)}$ or AUC) available for both treatments for the given analyte under consideration (for either ticagrelor or AR-C124910XX) in order to be included in a specific analysis; a subject may therefore be included in one or two comparisons for a given analyte and parameter.

The ratios of C_{max} , $AUC_{(0-t)}$ and AUC of both ticagrelor and AR-C124910XX will be obtained using a two-sided 90% CI approach based on an analysis of variance (ANOVA) model including fixed effects for treatment, sequence, period and subject within sequence. For exploratory purposes, the ANOVA as outlined here will be repeated with a random effect of subject within sequence. Additionally, the 90% CI for the difference in t_{max} will be calculated.

Bioequivalence may be concluded if the 90% CI of the ratios for both C_{max} and $AUC_{(0-t)}$ for both analytes are contained completely within the limits of 0.80-1.25.

Primary PK parameters will be log-transformed prior to analysis. The estimated treatment differences and the 90% CIs on the log scale will be back-transformed to obtain the geometric mean ratios for each pair of treatments. The least squares means (and 95% CIs for each), geometric mean ratios and 90% CIs will be tabulated for each treatment and analyte (ticagrelor and AR-C124910XX). The same ANOVA model will be applied to $t_{/2\lambda z}$, kel and MRT using log-transformed values [2].

In the analyses no adjustments will be made for multiple comparisons.

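### An entirely BLQ profile is excluded whatever its product or cause, so an unexplained failure of an OD dose, unlikely as it is, could not count in the bioequivalence decision

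*Protocol*

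**What the plan says.** The primary objective (protocol section 6.1) is "To evaluate bioequivalence of ticagrelor OD tablets when administered with water and without water, compared to ticagrelor IR tablets". The products are therefore judged as administered, including the OD tablet taken with saliva only (section 8.6).

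On profiles without a measurable concentration, section 11.9.2 says: "If an entire concentration-time profile is BLQ, the profile will be excluded from the PK analysis". It names no product and sets no condition.

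The PK analysis set (section 11.3.2) takes subjects "for whom at least one of the primary PK parameters, for a given analyte, can be calculated for at least two treatment periods", one of them the Reference period. Section 11.9.4 adds: "Subjects must have the primary PK parameter" for both treatments of the pair. It also says "Primary PK parameters will be log-transformed prior to analysis". Bioequivalence may be concluded if the 90% intervals for Cmax and AUC(0-t), for both analytes, "are contained completely within the limits of 0.80-1.25".

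Exclusions are documented with reasons (section 11.3.2) and listed (section 11.6). Data of subjects outside the PK analysis set are listed but kept out of the descriptive and inferential statistics (section 11.9.3). Section 11.2.1 sends BLQ handling back to section 11.9.2, and section 11.1 foresees no separate SAP.

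**The concern.** The exclusion is made on the outcome itself. The other grounds in section 11.3.2 (early vomiting, pre-dose carry-over, a major deviation) each point to something other than the product's performance. The all-BLQ rule is triggered by nil exposure alone.

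Dosing is supervised, with a check of mouth and hands (section 8.8). A profile without measurable drug after a confirmed OD dose would therefore be evidence about the tablet, and strong evidence against equivalent bioavailability. Removing it pulls the ratio toward 1 and narrows the interval. The analysis then answers whether the products are equivalent among doses that delivered measurable drug, which is narrower than the stated objective. The risk is a declaration of bioequivalence that passes over a complete release or absorption failure.

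**Working it through.** **Inputs from the protocol.** Within-subject CV at most 24%, 30 evaluable and 42 randomized subjects, and "a two-sided 90% confidence interval (CI) for the ratio of" Cmax (section 11.4); limits 0.80-1.25 (section 11.9.4).

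**Assumptions.** True ratio 1.00 in all other subjects and one all-BLQ Test profile. The documents give neither the LLOQ nor a typical Cmax, so the ratio q = usual Cmax/LLOQ is varied from 20 to 500.

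**Step 1: the plan's own figure.** The log-scale within-subject SD is sqrt(ln(1 + 0.24²)) = sqrt(ln 1.0576) = 0.2366, and the SE of a treatment difference is 0.2366·sqrt(2/n). Two one-sided tests with n − 2 df at n = 30 give power 0.945 at a true ratio of 1.00, 0.861 at 0.95 and 0.869 at 1.05. The smallest n for 90% is 26, 35 and 34 respectively. The protocol states no true ratio, so 30 cannot be uniquely reproduced; 26 rounded up to a multiple of six sequences gives 30. The point below does not depend on this.

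**Step 2: shift in the estimate.** Keeping the profile at the LLOQ replaces one log difference, expected to be 0, by −ln q. The geometric mean ratio is multiplied by q^(−1/n). As a share of the log margin ln 1.25 = 0.2231, the shift is ln(q)/(n·0.2231). For q = 20 and n = 30: ln 20 = 2.996, 2.996/30 = 0.0999, exp(−0.0999) = 0.905, and 0.0999/0.2231 = 45%.

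**Step 3: widening of the interval.** The SD of the paired log differences is 0.2366·sqrt(2) = 0.3347, variance 0.112. One outlying value of −ln q adds about (ln q)²/n to the sample variance.

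- n = 30, q = 20: 0.112 + 8.974/30 = 0.411, SD 0.641, SE 0.641/sqrt(30) = 0.117. With t = 1.701 the typical interval is exp(−0.0999 ± 0.199), about 0.74 to 1.10. It fails at the lower limit.
- n = 42, q = 20: 0.112 + 8.974/42 = 0.326, SD 0.571, SE 0.088. With t = 1.684 and a mean of −2.996/42 = −0.0713 the interval is about 0.80 to 1.08, right at the limit.

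**Step 4: chance that one Cmax interval lies within 0.80-1.25 (simulated paired log differences).**

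| Handling of the one profile | n=30: ratio | n=30: passes | n=42: ratio | n=42: passes |
|---|---|---|---|---|
| Excluded | 1.00 | 94% | 1.00 | 99% |
| Kept, q = 20 | 0.905 | 9% | 0.931 | 53% |
| Kept, q = 50 | 0.878 | 0.2% or less | 0.911 | 17% |
| Kept, q = 100 | 0.858 | 0% | 0.896 | 4% |
| Kept, q = 500 | 0.813 | 0% | 0.862 | 0% |

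At n = 30 the shift uses 45% (q = 20) to 93% (q = 500) of the log margin. A simulation of the pairwise model with fixed period and subject effects (n − 3 df) agrees: 93% against 10% (q = 20) and 0% (q = 100) at n = 30, and 99% against 52% and 4% at n = 42.

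**Step 5: does another provision restore the profile?** No. Sections 11.3.2, 11.6 and 11.9.3 make the removal visible, but none returns the profile to the interval or provides an analysis that keeps it.

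**The case against.** The strongest objection is that the sentence is not the only cause. Section 11.9.2 sets BLQ values before the first quantifiable concentration to zero, so Cmax would be zero and could not be logged. The same section requires three consecutive quantifiable concentrations for an AUC. Without the sentence, the profile would still drop out. This stands. It means that deleting the sentence is no remedy and that a stated value is needed.

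Second, the event is hypothetical. A 90 mg dose is expected to give adequate exposure (section 7.4), 14 samples are taken per period, and no rate of failure is given. This also stands: without such a profile nothing is biased.

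Third, the size depends on a convention, the value at the LLOQ, and on an assumed Cmax/LLOQ. That is true, and the range is shown for this reason. A reader might infer that one such profile is always enough to reverse the conclusion. The figures do not support that: with 42 subjects and q = 20 the interval still passes slightly more often than not.

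Fourth, the rule is product-neutral, disclosed in listings, and may leave the subject in the other comparison. Neutral wording does not cancel the effect when it is a Test profile that fails, and disclosure does not change the decision rule.

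**Conclusion.** The point holds as a conditional one. As written, the protocol would leave an unexplained all-BLQ profile after a confirmed OD dose out of the bioequivalence decision, and the effect would run toward equivalence. If that happened, the chance that one Cmax interval passes would be about 94% (n=30) or 99% (n=42), against 9% to 0% or 53% to 0% with the profile kept at the LLOQ. This rests on a CV of 24%, a true ratio of 1.00 elsewhere, a single failure, and an assumed Cmax/LLOQ of 20 to 500. The figures concern one interval; the full rule needs Cmax and AUC(0-t) for both analytes.

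It would go too far to say that the planned result is biased as it stands: the protocol gives no reason to expect such a profile. What can be said is that the rule depends on the outcome, is fixed in advance without regard to cause, and can be repaired at almost no cost.

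**What to change.** Amend section 11.9.2 as follows.

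- An all-BLQ profile, Test or Reference, is excluded without further analysis only when a documented cause unrelated to product performance explains it: a dosing, sampling or assay error. The cause may be found on investigation after the concentrations are seen.
- For an unexplained all-BLQ profile, a supplementary analysis of Cmax and AUC(0-t) keeps it, with Cmax set to the LLOQ and AUC(0-t) to a fixed LLOQ-based value. That value is written into the section beforehand, as an explicit exception to the three-concentration rule. The result is reported beside the analysis without the profile.
- If the unexplained profile is a Test profile, bioequivalence is not concluded from the exclusion analysis alone. Section 11.9.4 should refer to this.

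The cost is a few sentences and one further model run per affected comparison, only if such a profile occurs; no more subjects or samples are needed. The downside is that the LLOQ value is a convention, and one true Test failure may prevent a bioequivalence conclusion for that comparison.

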11.9.3. Presentation of pharmacokinetic data

A listing of PK blood sample collection times as well as derived sampling time deviations will be provided. Plasma concentrations and PK parameters will be summarized by treatment using appropriate descriptive statistics. Where possible, the following descriptive statistics will be presented: n, geometric mean, geometric CV, arithmetic mean, arithmetic SD, median, minimum and maximum. The correlation coefficient for determining kel will be estimated together with time-points used. For t_{max} , only n, median, minimum and maximum will be presented.

The ratios of C_{max} , $AUC_{(0-t)}$ and AUC of Test product to those of Reference product in each individual and analyte will be calculated.

The geometric mean is calculated as the exponential of the arithmetic mean calculated using log-transformed data.

The geometric CV% is calculated as $100 \cdot \sqrt{(\exp(s^2)-1)}$ where s is the SD of the log transformed data.

Individual PK parameters will be presented to three significant figures, with the exception of t_{max} which will be presented to two decimal places. Values >1000 in either the concentration data or PK parameter data will be presented to the nearest integer. For concentration and PK parameters summary data, the arithmetic mean, geometric mean, SD, median, minimum and maximum values will be reported to three significant figures and CV% to one decimal place.

Plasma concentrations that are BLQ or if there are missing values (e.g., no result [NR]) will be handled as follows:

- Where there is NR, these will be set to missing.
- At a time-point where less than or equal to 50% of the values are BLQ, all BLQ values will be set to the LLOQ, and all descriptive statistics will be calculated.
- At a time-point where more than half (but not all) of the values are BLQ, the arithmetic
 and geometric mean, SD, geometric mean and CV% will be set to Not Determined (ND).
 The maximum value will be reported from the individual data, and the minimum and
 median will be set to BLQ.
- If all values are BLQ at a time-point, no descriptive statistics will be calculated for that time-point. Not applicable (NA) will be written in the field for standard deviation and CV% and BLQ will be written in fields for arithmetic mean, geometric mean, minimum, median, and maximum.
- The number of BLQ values (n below LLOQ) will be reported for each time-point.

Data from subjects excluded from the PK analysis set will be included in the data listings, but not in the descriptive statistics or in the inferential statistics.

Individual plasma concentrations versus actual time will be plotted in linear and semi logarithmic scale with all treatments overlaid on the same plot and separate plots for each subject and analyte. Plots will be based on the safety analysis set.

Combined individual plasma concentration versus actual times will be plotted in linear and semi logarithmic scale. Plots will be grouped by treatment separately for each analyte, based on the PK analysis set.

Arithmetic mean plasma concentration (±SD) versus nominal sampling time will be plotted in linear and semi logarithmic (no SD presented) scale with all treatments overlaid on the same figure and separate plots for each analyte.

For mean plots, BLQ values will be handled as described for the summary tabulations; for individual plots BLQ values will be set to missing. All mean plots will be based on the PK analysis set.

